11.7 Reporting Safety Reports to Investigators

CCTG will notify Investigators of all Safety Reports (Serious Adverse Events (SAEs) from this trial and Safety Updates (SUs) from other clinical trials) that are reportable to regulatory authorities in Canada as reported to the CCTG. This includes all serious events that are unexpected and related (i.e. possibly, probably, or definitely) to protocol treatment. The reports will be posted to the CCTG trial IND 216 web-based safety monitoring utility.

Investigators must notify their Research Ethics Boards (REBs) of events which involve corrective action(s) to be taken as a result of the event(s) such as protocol and/or informed consent changes. The date of REB Submission for these SAEs and SUs will need to be entered into the CCTG trial IND 216 web based safety monitoring utility and documentation of REB submission must be retained in the study binder on site. The REB submission template provided by CCTG can be used to assist with tracking, submission, filing and monitoring.

The submission of events to your ethics board should be done as soon as possible (we suggest within 30 days). REB submissions greater than 90 days from the date of notification will be regarded as delinquent and a major deficiency will be assigned. These safety reports are to be filed in the trial files on site.

12.0 PROTOCOL TREATMENT DISCONTINUATION AND THERAPY AFTER STOPPING

12.1 Criteria for Discontinuing Protocol Treatment

Patients may stop protocol treatment in the following instances:

- Intercurrent illness which would, in the judgement of the investigator, affect assessments of clinical status to a significant degree, and require discontinuation of protocol therapy.
- Unacceptable toxicity as defined in Section 8.0.
- Progression or disease recurrence as defined in Section 10.0.
- Request by the patient.
- Completion of therapy as outlined in Section 8.0. Efforts should be made to maintain the investigations schedule and continue follow-up, even if patients discontinue protocol treatment prematurely and/or no longer attend the participating institution.

12.2 Duration of Protocol Treatment

(see Section 10.0 for response definition)

- For patients who achieve a complete or partial response, therapy will continue until objective disease progression or unacceptable toxicity, whichever occurs first.
- For stable patients, therapy will continue for a maximum of 6 cycles (24 weeks). Patients who have no evidence of tumour shrinkage at this point should go off therapy and receive other treatment at the investigator's discretion.
- Patients who progress (treatment failure) will go off study at the time progression is documented clinically and/or radiographically.

12.3 Therapy After Protocol Treatment is Stopped

At the discretion of the investigator.

12.4 Follow-up Off Protocol Treatment

See Section 9.3.

13.0 CENTRAL REVIEW PROCEDURES AND TISSUE COLLECTION

13.1 Central Radiology Review

There will be no central radiology review for this study.

13.2 Central Pathology Review

There will be no central pathology review for this study.

AMEND #1: 2015-OCT-22; AMEND #2: 2016-JAN-04

14.0 STATISTICAL CONSIDERATIONS

14.1 Objectives and Design

This is a single arm, open label, phase II study designed to assess the efficacy and toxicity of buparlisib in patients with relapsed and refractory chronic lymphocytic leukemia. The primary endpoint is objective response rate. Secondary end points include duration of response and progression-free survival.

14.2 Sample Size and Duration of Study

PI3K Inhibitor Naïve Cohort

The null hypothesis at which buparlisib will be considered of no value in this disease is an overall response rate of $\leq 5\%$. The alternative hypothesis at which the drug will be considered worthy of further study is $\geq 30\%$. Enrolment of 12 evaluable patients is required to test this hypothesis with a one-sided α of 0.1 and 80% power.

According to the Simon 2 stage design, 5 patients will be enrolled in the first stage. If at least one PR or CR is observed, then a total of 12 patients will be enrolled. When 2 or more patients among 12 evaluable patients achieve CR or PR, the null hypothesis will be rejected.

Exploratory Cohort

Outcomes of individuals previously treated with alternative PI3 kinase inhibitors will be presented descriptively. It is anticipated these numbers will be small, in which case any observed CR or PR will be of interest and considered worthy of further study. If for example 8 patients are enrolled, this would enable detection of a 5% versus 20% overall response rate with 53% power at a one sided α of 0.1. A maximum of 17 individuals will be enrolled on this exploratory cohort.

Overall

Accrual of up to 29 patients overall is anticipated to take place over 24 months. Follow-up of 6 months will be required after the last patient is enrolled. Thus, total duration of study is expected to be 30 months.

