Statistical analysis plan for I216

June 28, 2017

By [name]

The analysis will be descriptive with continuous variable measured by mean and SD or median and range and categorical variable measured by percentage.

Table 1 to table 12 are the same as the meeting book table and no additional program is needed.

Table 13: Duration of response. Median (Min, Max) of the duration of the response will be reported for patients with CR/CRu and PR.

Response duration will be measured from the time measurement criteria for CR/PR (whichever is first recorded) are first met until the first date that recurrent or progressive disease is objectively documented, taking as reference the smallest measurements recorded on study (including baseline).

Figure 1. Waterfall plot for tumour shrinkage

Figure 2. KM plot for PFS

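### The exploratory cohort's 53% power with 8 patients is not attained by any response count within one-sided alpha 0.1; the exact figure is 49.7%

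*Protocol*

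**What the plan says.** Protocol section 14.2 treats two cohorts.

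- **PI3K inhibitor naïve cohort.** This has a formal design with whole-number cut-offs: "According to the Simon 2 stage design, 5 patients will be enrolled in the first stage", at least one response is needed to go on to 12, and 2 or more responses among 12 reject the null hypothesis. The stated properties are one-sided alpha 0.1 and 80% power for 5% versus 30%.
- **Exploratory cohort.** "Outcomes of individuals previously treated with alternative PI3 kinase inhibitors will be presented descriptively". Numbers are expected to be small, and in that case "any observed CR or PR will be of interest and considered worthy of further study". The example then follows: "If for example 8 patients are enrolled, this would enable detection of a 5% versus 20% overall response rate with 53% power", with alpha set one-sided at 0.1. The cohort is capped at 17. No response count and no calculation method accompany the 53%.

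The SAP adds nothing that would settle which rule is meant. It states "The analysis will be descriptive with continuous variable measured by mean and SD" and gives no test, cut-off or power for this cohort.

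**The concern.** A power figure describes a rule for declaring a result. With 8 patients the outcome is a whole number of responders, so the available error rates move in large steps and only a few combinations of alpha and power exist. A printed pair of 10% and 53% with no cut-off invites the question of which count it belongs to.

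The only signal the paragraph names is any response at all, and it sits just before the power sentence. A reader could easily attach the alpha of 0.1 to that signal. The protocol does not make that link and this point does not assume it, but nothing in the text prevents the reading.

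What is at stake is accurate reporting: whether the stated power is one the cohort can have, and whether readers understand how often a lone response would appear if the drug had little activity in these patients.

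**Working it through.** **Inputs**, all from Protocol section 14.2, Exploratory Cohort: n = 8, null rate p0 = 0.05, alternative rate p1 = 0.20, one-sided alpha 0.1, stated power 53%.

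**Step 1: reproduce the stated figure.** The arcsine normal approximation is

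power = Φ( 2[asin√p1 − asin√p0]·√n − z₀.₉₀ ).

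Here asin√0.20 = 0.4636 and asin√0.05 = 0.2255, so 2 × 0.2381 × 2.8284 = 1.3471. Subtracting 1.2816 leaves 0.0655, and Φ(0.0655) = 0.526, which rounds to 53%. Other normal approximations miss: 64.1% with null and alternative variances, 41.3% with the alternative variance only, 74.7% with the null variance only. The arcsine formula is therefore the likely source, but that is an inference because the protocol names no method.

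**Step 2: exact power for every usable count.** With X ~ Binomial(8, p), P(X = 0) = (1 − p)⁸, P(X = 1) = 8p(1 − p)⁷ and P(X = 2) = 28p²(1 − p)⁶.

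At p = 0.05:
- P(X = 0) = 0.6634, so P(X ≥ 1) = 0.3366
- P(X = 1) = 0.2793, so P(X ≥ 2) = 0.0572
- P(X = 2) = 0.0515, so P(X ≥ 3) = 0.0058

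At p = 0.20:
- P(X = 0) = 0.1678, so P(X ≥ 1) = 0.8322
- P(X = 1) = 0.3355, so P(X ≥ 2) = 0.4967
- P(X = 2) = 0.2936, so P(X ≥ 3) = 0.2031

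| Rule (of 8) | Exact alpha | Exact power |
|---|---|---|
| 1 or more | 33.7% | 83.2% |
| 2 or more | 5.7% | 49.7% |
| 3 or more | 0.6% | 20.3% |
| 4 or more | 0.04% | 5.6% |

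The lowest count within alpha 0.1, and so the most powerful, is 2 or more. Its power is 53% − 49.7% = 3.3 points short of the stated value, which is too large for rounding.

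**Step 3: how many patients would deliver 53%?** The best count within alpha 0.1 is 2 or more for n = 7 (4.4% / 42.3%), n = 8 (5.7% / 49.7%) and n = 9 (7.1% / 56.4%). The smallest cohort that reaches 53% is therefore 9. Put differently, the rule of 2 or more out of 8 reaches 53% only at a true response rate just above 21% (52.6% at 21%, 54.0% at 21.5%).

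**Step 4: the any-response signal.** If the true rate is 5%, at least one response appears with probability 1 − 0.95⁸ = 33.7% among 8 patients, and 1 − 0.95¹⁷ = 58.2% at the cap of 17. This signal cannot be the rule behind an alpha of 0.1.

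**Step 5: the neighbouring design as a benchmark.** For the naïve cohort (stop at 0 of 5, reject at 2 or more of 12), the rejection probability is P(2 or more of 12) − P(0 of 5) × P(2 or more of 7).

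- At 5%: 0.1184 − 0.7738 × 0.0444 = 0.0840
- At 30%: 0.9150 − 0.1681 × 0.6706 = 0.8023

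Exact alpha 8.4% and power 80.2% agree with the stated 0.1 and 80%. The figures for the primary cohort do hold for whole-number rules.

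**The case against.** The strongest reply is that the figure is not wrong, only approximate. The arcsine formula returns it from the protocol's own inputs, and the sentence states no cut-off, so a whole-number rule is something the reader brings to it. It can also be said that 53% at a nominal 10% is being compared with 49.7% at an attained 5.7%, so part of the gap is unused alpha. A randomised exact test that spends the full 10% would reject on exactly one response with probability (0.1 − 0.0572)/(0.3366 − 0.0572) = 0.153. Its power would be 0.4967 + 0.153 × (0.8322 − 0.4967) = 54.8%, above the stated value. Finally, the sentence is an illustration in a descriptive cohort, and 50% and 53% both tell the reader that 8 patients are too few.

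Most of this stands as a limit on importance. It does not rescue the figure. The expected number of responses under the null is 8 × 0.05 = 0.4, and the attainable alpha jumps from 5.7% to 33.7%, so treating the count as continuous with alpha exactly 0.1 describes no rule anyone could apply to 8 patients. The protocol describes no randomised test. Knowing where a number probably came from does not make it a property of the cohort.

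**Conclusion.** The concern holds and is minor. No count of responders out of 8 combines 53% power with a type I error of at most 10%. The best rule within that limit has 49.7%, an overstatement of 3.3 points. The conclusion rests on independent patients with a common response rate, on the 5% and 20% rates given in the protocol, and on any rule being a count of responders. The attribution to the arcsine approximation is an inference and the conclusion does not depend on it. No decision or sample size rests on the 53%, and the naïve cohort's design is unaffected.

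**What to change.** In Protocol section 14.2, Exploratory Cohort, replace the example sentence with:

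> With 8 patients, at least one response would be seen with probability 34% if the true ORR is 5% and 83% if it is 20%; observing 2 or more of 8 has exact one-sided alpha 5.7% and power 50%.

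The rest of the paragraph stays: the descriptive status, the statement about any response, and the cap of 17. The 2-or-more figures describe what 8 patients can show; they are not a decision threshold, and a short clause saying so would avoid confusion with the any-response statement. If the sponsor prefers no power statement in a descriptive cohort, deleting the example sentence also removes the error, but readers then lose the information on how often a lone response would arise at a 5% rate.

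The cost is one sentence, with no added patients and no change to the primary cohort. The printed power becomes slightly less favourable, and the 34% chance of at least one response at a 5% rate is shown openly.

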14.3 Safety

Adverse events will be monitored on an ongoing basis by the central office and their frequencies reported annually at investigators' meetings. Adverse events will be categorized using the NCI Common Terminology Criteria for Adverse Events (CTCAE) or other protocol specified criteria for hematological and psychiatric toxicity (see Appendix V). The worst event for each patient in each category or subcategory will be described. Both events related and unrelated to treatment will be captured.

Clinical and laboratory data will be tabulated and compared to normal ranges for the institution.

14.4 Correlative Studies

Secondary objectives related to correlative studies are exploratory in nature. Peripheral blood will be assayed to investigate the correlation, if any, between response and potential biomarkers. Chi-square (categorical results) or regression models (continuous results) will be used to explore the relationship between laboratory findings and response or early progression.

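### Section 14.4 names chi-square with no variant and no small-count rule, although every 2×2 table within either cohort has an expected count below 5

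*Protocol*

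**What the plan says.** Protocol Section 14.4 gives the method in one sentence: "Chi-square (categorical results) or regression models (continuous results) will be used to explore the relationship between laboratory findings and response or early progression". It does not say whether the test is uncorrected (Pearson), Yates-corrected or likelihood-ratio. It names no exact alternative and sets no significance level. The same section states that "Secondary objectives related to correlative studies are exploratory in nature".

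Section 14.2 fixes the table sizes. For the PI3K-inhibitor-naïve cohort, "Enrolment of 12 evaluable patients is required to test this hypothesis with a one-sided α of 0.1 and 80% power". The exploratory cohort has a maximum of 17, and overall "Accrual of up to 29 patients overall is anticipated to take place over 24 months". The design response rates are 5% (null) and 30% (alternative).

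Section 17.2 plans a univariate analysis of gene copy number and names no test. It cites a 6% frequency of PIK3CA amplification in an earlier, mostly untreated CLL series. The SAP describes the analysis as descriptive and names no biomarker test; its Tables 1 to 12 are only referred to, not shown. Section 14.4 is therefore the only text that names a test for categorical markers.

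**The concern.** Chi-square p-values rest on a large-sample approximation, usually trusted when every expected count is at least 5. Here the tables are small and the design anticipates few responders, so the approximation is poor for most tables the trial can produce. The choice between the uncorrected and corrected forms, which the protocol leaves open, can then move a result across 0.05.

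What is at stake is how the biomarker results will be read. They serve a listed secondary objective (Section 1.2.3). The rationale in Section 17.1.1 speaks of confirming that two pathway proteins predict clinical response, with a view to selecting patients for PI3K inhibitors. A nominal p just below 0.05 from a handful of responders could be given weight that it does not carry.

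**Working it through.** **Inputs.** N = 12, 17 (maximum) and 29 (pooled maximum), and response rates of 5% and 30%, from Section 14.2. Amplification frequency of 6%, from Section 17.2. Marker splits, tables of 20 patients and response rates other than 5% and 30% are assumptions, because the documents fix no cut-offs. They also give no expected rate of early progression.

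**1. The plan's own design reproduces.** Of the naïve cohort, Section 14.2 says "5 patients will be enrolled in the first stage"; enrolment continues with at least 1 response. The final rule is: "When 2 or more patients among 12 evaluable patients achieve CR or PR, the null hypothesis will be rejected". The exact rejection probability is the sum over x = 1 to 5 of P(X₁ = x)·P(X₂ ≥ 2 − x), with X₁ ~ Bin(5, p) and X₂ ~ Bin(7, p).
- p = 0.05: 0.084, within the stated 0.10.
- p = 0.30: 0.802, matching the stated 80%.

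At a 30% response rate the most likely count in 12 patients is 3 responders (probability 0.24).

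**2. Expected counts.** The smallest expected count is (smaller marker group × smaller outcome group)/N. Its largest attainable values are:
- N = 12: 6×6/12 = 3.0
- N = 17: 8×8/17 = 3.8
- N = 19: 9×9/19 = 4.3
- N = 20: 10×10/20 = 5.0
- N = 29: 14×14/29 = 6.8

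No table of 19 or fewer can reach 5. At N = 29 with 9 responders (about 30%) and a 14/15 marker split, it is 14×9/29 = 4.3; with 10 it is 4.8; with 11 it is 5.3. All four counts reach 5 only with 11 to 18 events and a near-even split. For amplification, 6% of 29 is about 2 patients, and 2×9/29 = 0.6.

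**3. One table, three p-values.** Take 3/6 responders against 0/6, so that |ad − bc| = 18 and the product of the margins is 6×6×3×9 = 972.
- Uncorrected: 12×18²/972 = 4.00, p = 0.046.
- Yates: 12×(18 − 6)²/972 = 1.78, p = 0.18.
- Fisher, two-sided: 2×C(6,3)/C(12,3) = 40/220, p = 0.18.

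**4. Other tables, uncorrected against Fisher.**
- 2/3 vs 0/9: 0.0073 against 0.0455 (6.2-fold)
- 1/1 vs 1/11: 0.0195 against 0.167 (8.5-fold)
- 2/2 vs 7/27: 0.029 against 0.089 (3.1-fold)
- 10/14 vs 4/15, with all expected counts above 5: 0.016 against 0.027 (1.7-fold)

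Among all tables with an uncorrected p between 0.01 and 0.05, the median ratio is 3.5 at N = 12, 2.3 at N = 17 and 1.9 at N = 29.

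**5. Conditional type I error at nominal 5%** (hypergeometric, margins fixed).
- 3 responders, 6/6 split: 2×20/220 = 18.2% uncorrected; Fisher 0%.
- 4 responders, 10/10 split: 2×210/4845 = 8.7%; Fisher 0%.
- 4 responders, 14/15 split: (1001 + 1365)/23751 = 10.0%; Fisher 4.2%.

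The Yates-corrected test gives 0% in all three. Neighbouring counts differ sharply for the uncorrected test: with the 6/6 split, 1 or 2 responders give 0%, 4 give 6.1% and 5 give 1.5%.

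**6. Averaged over the responder count.** With those splits fixed and response rates from 5% to 50%, the size of the uncorrected test is 0.3–6.8% (N = 12), 0.1–4.2% (N = 20) and 0.5–6.2% (N = 29). When the marker split also varies (prevalence 6%, 20% or 50%), the range at N = 12 and 29 is 0.6–5.9%.

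**The case against.** The strongest reply is that little depends on this test. The section labels the analyses exploratory, sets no alpha, and attaches no decision to them. The SAP is descriptive. The main markers (MTT sensitivity and protein levels, Section 17.1) are measured as levels, which Section 14.4 sends to regression; chi-square applies only to categorical or dichotomised markers. All of this stands, and it sets the priority. The confirming language in Section 17.1.1 is rationale and creates no confirmatory test.

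A reader might also infer three stronger things that the documents do not support.
- *That the expected counts are always too small.* Section 14.4 also covers early progression, which may be common, and a pooled table of 20 to 29 with a near-even split can meet the condition.
- *That the test will generate false markers several times too often.* The inflation belongs to particular margins. Averaged over responder counts the size is near or below nominal, and part of the gap to Fisher is Fisher's own conservatism.
- *That associations are overstated.* Only p-values are affected; response rates and odds ratios are unchanged.

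Finally, the uncorrected form is one reading. Under Yates the anticonservatism disappears in the examples above. That does not rescue the wording, because the protocol does not say which form will be used.

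**Conclusion.** The point holds in limited form and is low priority. Section 14.4 names an unspecified large-sample test with no small-count provision. Within either cohort the usual condition cannot be met, and pooled it fails at response rates up to about 30%.

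For particular tables the uncorrected p-value is about 2- to 8-fold below Fisher's, and conditional type I error can reach about 18% (3 responders of 12, 6/6 split). Averaged over responder counts it stays at or below about 7%. The more practical defect is the open choice of variant: 0.046 or 0.18 for the same data, both consistent with the protocol.

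The figures for the uncorrected test assume that reading of the protocol, 2×2 tables, a two-sided nominal 5% level (the protocol sets none) and the marker splits shown.

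**What to change.** In Section 14.4, or in a line added to the SAP:
- Replace chi-square with one exact test named in advance: Fisher's exact, or a mid-p or unconditional exact test.
- Report response rates by marker group with exact confidence intervals.
- For continuous markers against response, specify exact or Firth logistic regression, since with only a few responders ordinary logistic regression is prone to separation.

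This is a wording change of a line or two, with no new data and no change to the design. The statistical cost is conservatism. With a 6/6 split of 12, Fisher's test cannot reach p < 0.05 with 4 or fewer responders: the most extreme table with 4 gives 2×15/495 = 0.061. Averaged over responder counts, its size there is at most 0.6%. The estimates and intervals should therefore carry the interpretation, whichever exact test is chosen.

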1.2 Secondary Objectives

- 1.2.1 To evaluate the safety and tolerability of buparlisib administered at 100 mg per day on a 28 day cycle, in patients with previously treated chronic lymphocytic leukemia.
- 1.2.2 To evaluate additional measures of efficacy including:
 - duration of response rate
 - progression free survival
- 1.2.3 To explore potential molecular factors which may be prognostic or predictive of response or of relapse including:
 - correlation between clinical response to buparlisib and MTT assay (cell viability assay) in B-CLL exposed ex-vivo to buparlisib
 - correlation between response to buparlisib and western blot and flow cytometry analysis of key proteins involved in the PI3K pathway
 - identification of mechanisms of resistance among patients who relapse after therapy with buparlisib
- 1.2.4 To prospectively validate a survival prediction scale.

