9.3 Evaluation After Protocol Treatment

All patients will be seen 4 weeks after the end of the last cycle (4 Week Post Treatment Report).

Patients whose treatment is permanently discontinued due to an adverse event or non-hepatic clinically significant laboratory value, should be followed as clinically indicated until resolved to \leq grade 2. See Section 8.4.3 for more detailed guidance on patients who discontinue study treatment due to hepatic toxicity.

Follow-up beyond the 4 week treatment report is not required for patients who go off protocol treatment with progressive disease, except to document ongoing toxicities (until resolved to \leq grade 2), late toxicities (including second malignancies) and death if within 30 days of last dose.

For patients who go off protocol treatment with objective CR, PR or SD ongoing, follow up including response assessment will be required every three months until relapse/progression (Follow-Up Report). If the patient starts new anticancer therapy, contact the study coordinator to discuss whether further follow-up is required.

For patients who go off protocol therapy with suspected PR or CR, an 8 week confirmatory response assessment including CT scanning will be required as per Sections 9.1 and 10.4, if not already performed.

A Death Report is only required if death occurs within 30 days of last dose or if patient dies before progression/relapse; due within 2 weeks of knowledge of death (see Appendix IV –Documentation for Study).

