10.7 Progression-Free Survival

Progression-free survival (PFS) is defined as the time from study entry until disease progression or death.

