17.2 PIK3CA Gene Amplification Analysis

PI3K mutations are well described in solid tumours (particularly in PIK3CA-the gene which encodes p110 α), however activating PI3K mutations are noticeably absent in B cell malignancies such as CLL [*Marincevic 2009; Ortiz-Maldonado 2015; Thorpe 2015*]. A recent study of 188 patients with CLL showed no point mutations in p110 α , - δ or - β isoforms, despite PI3K pathway constitutive activation [*Brown 2012*]; however, the same study demonstrated that amplifications of the PIK3CA locus were present in 6% of CLL patients (with 80% of the CLL cohort investigated being treatment naïve). Thus, gene amplification will be studied as a mechanism for PI3K pathway activation in this relapsed/refractory CLL population, by investigation of the copy number status of the genes PIK3CD and PIK3CA, which encode the p110 δ and p110 α isoforms respectively. Gene amplification will be measured using digital PCR, a highly sensitive and accurate methodology, in all patients treated on the IND 216 trial, both prior to therapy and after disease progression correlating with development of drug resistance.

Univariate analysis will be attempted to investigate for any association of copy number variation with known clinical characteristics and prognostic factors (age, gender, number of prior lines of therapy, cytogenetics, unmutated IgHV status and response and duration of response to buparlisib).

AMEND #1: 2015-OCT-22

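### Section 14.4 relates biomarkers to relapse only through an undefined early progression, although PFS time is a defined endpoint that could be analysed by marker at almost no cost

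*Protocol*

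**What the plan says.** Protocol objective 1.2.3 is "To explore potential molecular factors which may be prognostic or predictive of response or of relapse including" three listed laboratory topics. The analysis is in Section 14.4: "Chi-square (categorical results) or regression models (continuous results) will be used to explore the relationship between laboratory findings and response or early progression". The same section states that "Secondary objectives related to correlative studies are exploratory in nature". It gives no time point for early progression, no type of regression, and no alpha or power.

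Time to progression is handled elsewhere. Section 10.7 says: "Progression-free survival (PFS) is defined as the time from study entry until disease progression or death". Section 14.1 lists PFS as a secondary endpoint. Section 9.3 has patients who stop treatment with ongoing CR, PR or SD assessed every three months until progression, with one qualification: "If the patient starts new anticancer therapy, contact the study coordinator to discuss whether further follow-up is required". Section 14.5 specifies Kaplan-Meier and a hazard ratio for the survival scale.

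Section 17.2 plans univariate analyses of PIK3CA and PIK3CD copy number against several factors, including "response and duration of response to buparlisib". The SAP lists "Figure 2. KM plot for PFS" but no analysis of any biomarker, so it does not settle what 14.4 leaves open.

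**The concern.** The objective concerns relapse, but the outcome named for it is early progression. With a categorical marker and a chi-square test, each patient must be placed in a category at some time point. A patient who progresses after that point is then scored the same as one who never progresses, and a patient censored before it has no valid category. Because the time point is not fixed, it could also be chosen after the data are seen.

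Section 17.2 does not fill the gap. Its only time-based outcome is duration of response, which exists only in responders. At the 30% alternative for the naive cohort that is 0.30 × 12 = 3.6 patients expected.

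At stake is a secondary, exploratory objective in at most 29 patients: a real association between a marker and relapse becomes easier to miss.

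**Working it through.** **The plan's own figure.** No power is stated for the correlative work. The nearest stated design is the Simon two-stage plan in Section 14.2 (5 then 12 patients, reject at 2 or more responses). P(reject) = P(at least 2 of 12) − P(0 of first 5) × P(at least 2 of last 7).
- At 5%: 0.1184 − 0.7738 × 0.0444 = 0.084.
- At 30%: 0.9150 − 0.1681 × 0.6706 = 0.802.

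This agrees with the stated one-sided 0.1 and 80%, and the present point does not affect it.

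**Inputs from the documents.** Up to 29 patients, of whom 12 are PI3K-inhibitor naive and at most 17 exploratory; 24 months of accrual and 6 months of further follow-up (14.2); CT at 8, 16 and 24 weeks, then every 12 weeks (9.1).

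**Assumptions not in the documents.** Exponential PFS with median 6, 9 or 12 months; binary marker split 50/50; hazard ratio (HR) 3; two-sided 5% test; *early* meaning by 24 weeks (5.52 months); administrative censoring C uniform on 6 to 30 months.

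**Share of observed progressions that fall after the cut.** With λ = ln 2 / median and no marker effect, share = 1 − [1 − exp(−5.52λ)] / [1 − E exp(−λC)].
- Median 6: 1 − 0.471/0.831 = 43%.
- Median 9: 1 − 0.346/0.713 = 51%.
- Median 12: 1 − 0.273/0.617 = 56%.

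**Closed-form check of power, n = 29, HR 3.** Group hazards are λ√3 and λ/√3.
- Median 6: 67% against 31% progress by 24 weeks; a two-proportion test has power of about 49%. With about 23 PFS events, log-rank power is Φ(√23 × ln 3 / 2 − 1.96) = Φ(0.67), about 75%.
- Median 12: 42% against 17%; about 32%. With about 18 events, Φ(√18 × ln 3 / 2 − 1.96) = Φ(0.37), about 64%.

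**Simulation, n = 29, HR 3, 24-week cut** (3,000 runs, log-rank calibrated to size, 30% responders). The first column is a further assumption: the share of non-responders censored at new therapy within 3 months after week 24.

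| Share censored | Log-rank, median 6/9/12 | Chi-square | Gain in points |
|---|---|---|---|
| 0% | 70/64/62% | 52/43/34% | 18/21/28 |
| 50% | – | – | about 13 to 19 |
| 100% | 59/53/44% | 55/44/33% | 4/9/11 |

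A repeat at medians 6 and 12 gave 73% against 57% and 63% against 35% with administrative censoring only (gains of 16 and 28 points), and gains of about 7 to 8 points when all non-responders are censored soon after week 24. Rounded over the runs, the gain is about 15 to 28 points in the first case and about 5 to 11 when most non-responders are censored at new therapy.

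**Smaller effect or sample.** At HR 2 with 100% of non-responders censored, the gain is about 1 to 6 points. At n = 12 and HR 3, it runs from about −2 to +8 points.

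**The case against.** The strongest objection concerns follow-up. A reader might infer that PFS time is available for every patient. The documents do not support that. Section 12.2 limits treatment of stable patients to 6 cycles (24 weeks) and lets those without shrinkage move to other treatment, and Section 9.3 then leaves further follow-up to a case-by-case discussion. Many later progressions in non-responders may go unrecorded or follow another drug. This stands, and it is why the smaller range is quoted beside the larger one. Under full censoring of this kind at HR 2 to 3, late events are about 22 to 34% of observed events, not 43 to 56%.

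A reader might also infer that 14.4 imposes a yes/no outcome on every marker. That follows only for categorical markers. The regression for continuous markers is unspecified, so Cox regression is not excluded; the defect there is that outcome and model are undefined.

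Nor can it be said that copy number is never related to failure in non-responders. Copy number is a laboratory finding measured in all treated patients, so 14.4 already relates it to early progression. What is missing is its relation to PFS time.

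The objection also notes that the relapse item listed under 1.2.3 is laboratory study of resistance in relapsed patients, and that no passage promises a test of markers against PFS. That is correct, although the list is not exhaustive and 14.4 itself takes up progression as an outcome. Finally, 29 is a ceiling: the exploratory cohort is expected to be small (the example is 8) and is to be presented descriptively, and the naive cohort can stop after 5. Asking who fails early on the drug is a legitimate question, so the cut deserves to be kept, with a definition.

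**Conclusion.** The point holds as a cheap improvement to an exploratory analysis. Section 14.4 names an undefined outcome for relapse and, for categorical markers, a test that discards progression times, when a defined time-to-event endpoint is available for most patients.

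The direction of the loss is clear at the maximum sample size; its size is not fixed by the documents. Under the assumptions listed, at n = 29 it ranges from about 15 to 28 points with administrative censoring only down to about 5 to 11 points when most non-responders are censored at new therapy. At n = 12 there is little or nothing to gain. Larger losses can be produced by assuming an earlier cut: at median 6 months, an 8-week cut gives chi-square 22% against log-rank 72%. That rests on a cut-off that no document states, so a claim that most of the power is lost is not supported. The calculations also assume proportional hazards and did not include strata for cohort.

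**What to change.** - **Section 14.4, and the SAP beside Figure 2:** add an exploratory analysis of PFS time (10.7) by marker. Use a log-rank test for categorical markers and single-covariate Cox regression for continuous ones, with permutation p-values or Firth penalisation because numbers are small. Stratify by cohort when the cohorts are pooled. State how PFS is censored when new anticancer therapy starts.
- **Early progression:** keep it as a descriptive secondary look, with a cut-off stated in advance and tied to the CT schedule (for example 24 weeks).
- **Section 17.2:** add PFS in all treated patients as an outcome for copy number, and keep duration of response as a description in responders.

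The cost is a few sentences in the protocol and SAP, with no new data, visits or patients. The downside is that a marker acting only on very early failure is shown better by the cut, which is why the cut is retained descriptively.
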